5.1.2. Fluid Overload

Similar to endothelin receptor antagonists (ERAs) in certain patient populations, including bosentan in advanced congestive heart failure and avosentan in advanced CKD, bardoxolone methyl treatment was found to be associated with an increased risk for fluid overload and heart failure hospitalizations in the BEACON trial, which enrolled patients with Stage 4 CKD (eGFR 15-29 mL/min/1.73 m²) and type 2 diabetes. The overall increased risk for fluid overload and heart failure events with bardoxolone methyl appeared to be limited to the first three to four weeks after initiation of treatment. Elevated BNP and prior hospitalization for heart failure were identified as risk factors that contributed to increased risk for these events. The increased risk for these events from bardoxolone methyl treatment had not been observed in six previous CKD studies, which were conducted mostly in patients with Stage 3b CKD (eGFR of 30-44 mL/min/1.73 m²), patients with hepatic dysfunction, cancer patients, or healthy volunteers.

Review of admission notes and narrative descriptions for heart failure hospitalizations in BEACON indicates that heart failure in bardoxolone methyl-treated patients was often preceded by rapid fluid weight gain (several kilograms within the first weeks of treatment initiation) and was not associated with acute renal decompensation or acutely reduced left ventricular contractility. Available data from BEACON and other studies suggest that bardoxolone methyl treatment can differentially affect hemodynamic status according to the clinical condition of patients and likely promotes fluid retention in patients with more advanced renal dysfunction and other recognized risk factors associated with heart failure at baseline.

In a Phase 2 dose-ranging study of the efficacy and safety of bardoxolone methyl in patients with pulmonary hypertension (LARIAT), risk mitigation procedures were employed to reduce the potential for bardoxolone methyl-induced fluid overload; these procedures excluded patients with the identified risk factors and ensured close monitoring for fluid retention within the first month of treatment. To date, the risk for acute fluid overload adverse events with bardoxolone methyl in late-stage CKD patients has not been observed in PAH patients.

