Each AE should be recorded to represent a single diagnosis. Accompanying signs (including abnormal laboratory test values or ECG findings) or symptoms should NOT be recorded as additional AEs. If a diagnosis is unknown, sign(s) or symptom(s) should be recorded as an AE(s). Changes in laboratory test values or ECG parameters are only considered AEs if they are judged to be clinically significant (*i.e.*, if some action or intervention is required or if the investigator judges the change to be beyond the range of normal physiological fluctuation). If abnormal laboratory test values or ECG findings are the result of pathology for which there is an overall diagnosis (*e.g.*, increased creatinine levels in renal failure), only the diagnosis should be reported as an AE.

Elective procedures (surgeries or therapies) that were scheduled prior to the start of AE collection are not considered AEs. These elective procedures should not be recorded as AEs, but should be documented in the patient’s source documents as elective (*e.g.*, elective periodontal surgery). However, if a pre-planned procedure is performed early (*e.g.*, as an emergency) because of a worsening of the preexisting condition, the worsening of the condition should be captured as an AE.

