The Sponsor or designee will notify regulatory agencies of any fatal or life-threatening unexpected events associated with the use of the study drug as soon as possible but no later than 7 calendar days after the initial receipt of the information. Initial notification will be followed by a written report within the timeframe established by the appropriate regulatory agency. For other SAEs that do not meet the fatal or life-threatening unexpected criteria, but are reported to be associated with the use of the study drug, Reata or designee will notify the appropriate regulatory agencies in writing within the timeframe established by those regulatory agencies. Reata or designee will provide copies of any reports to regulatory agencies regarding serious and unexpected SAEs to the investigators for review and submission to their institutional review board (IRB or Ethics Committee (EC, as appropriate.

Principal investigators are responsible for informing their IRB/EC of any SAEs at their site. SAE correspondence with regulatory authorities or IRBs/ECs must be submitted to the Sponsor or designee for recording in the study file.

Note that the following adverse events which are commonly observed in this patient population will not be reported to regulatory authorities as individual expedited reports, except in unusual circumstances.

- Shortness of breath
- Lightheaded/dizzy

- Syncope
- Chest pain
- Palpitations
- Fatigue
- Edema/fluid retention
- Exertional dyspnea
- Hypoxemia

These events will be reviewed on a regular basis in aggregate and will be reported in an expedited manner if a safety signal is detected. Regular safety study updates will be reported to regulatory authorities according to local guidelines.

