2.2. Study design

The CATALYST study will randomize approximately 130 patients with CTD-PAH. This number may be increased to approximately 200 patients depending on the results of a blinded sample size re-calculation.

Patients who meet all inclusion criteria and no exclusion criterion and have satisfied screening evaluations will be randomized 1:1 to receive either placebo or bardoxolone methyl administered once daily for 24 weeks. Patients randomized to placebo will remain on placebo throughout the study and undergo sham titration. Patients randomized to bardoxolone methyl will start at 5 mg

[figure not shown]
and will dose-escalate to 10 mg at Week 4, unless contraindicated clinically. Dose de-escalation is permitted during the study if indicated clinically.

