The MedDRA dictionary will be used to classify all AEs reported during the study by system organ class (SOC) and preferred term (PT). All summary tables will include counts of patients with treatment-emergent adverse events (TEAEs). TEAEs are defined as those AEs that have an onset time either at or after the start of study drug administration and no more than 30 days after the last dose of study drug is administered. Furthermore, TEAEs may be AEs ongoing at the time of study drug initiation that increase in severity or become closer in relationship to study drug administration during the treatment period. AEs with missing start dates, but with stop dates either overlapping into the treatment period or missing, will be considered TEAEs.

An overall summary of TEAEs will be presented with the number and percentage of patients having a TEAE, a serious TEAE, a TEAE leading to study discontinuation, a TEAE with an outcome of death, a TEAE related to study drug (definitely, probably, or possibly related), or a severe TEAE. The overall incidence of TEAEs will be summarized by SOC and by SOC and PT

using the number and percentage of patients reporting an event and the number of events reported. The incidence of serious TEAEs and TEAEs leading to study discontinuation will be summarized in a similar manner. TEAEs will also be summarized by maximum severity (mild, moderate, or severe) and assessed relationship to study drug with the percentage of patients in each category. A TEAE with missing severity or relationship will be considered severe or related, respectively. If more than one TEAE is recorded for a patient within any SOC or PT, the patient will only be counted once. Serious TEAEs, TEAEs leading to study discontinuation, and TEAEs with an outcome of death will be presented in separate listings.

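### SAP 12.2 has no grouped fluid overload / heart failure category and no summary by time of onset, so an early excess could be split across terms and pooled with later events

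*SAP*

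**What the plan says.** **Adverse event tables.** SAP 12.2 (Adverse events and serious adverse events) is readable in full. It says: "The overall incidence of TEAEs will be summarized by SOC and by SOC and PT". A patient counts once within each SOC or PT. Serious TEAEs and TEAEs leading to study discontinuation get the same tables. TEAEs are also tabulated by maximum severity and by relationship, and serious, discontinuation and fatal TEAEs are listed. An event is treatment-emergent from first dose until "no more than 30 days after the last dose of study drug is administered". Later events are tabulated separately as off-treatment. No group of related terms, onset interval or time-to-onset summary is defined.

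**The risk.** Protocol 5.1.2 (Fluid Overload) describes more fluid overload and heart failure hospitalisation on bardoxolone methyl in a trial "which enrolled patients with Stage 4 CKD" and type 2 diabetes. The excess "appeared to be limited to the first three to four weeks after initiation of treatment". The section adds that the risk seen "in late-stage CKD patients has not been observed in PAH patients" to date.

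**What the protocol does about it.** Protocol 9.1.1 cites this risk for limits on eGFR, BNP and left-sided heart disease, and for daily home weights in the first 8 weeks with action at a gain of 2.3 kg. Protocol 9.10.9 keeps the home weights out of the eCRF.

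**Recording.** Protocol 11.6 asks for one diagnosis per event, or the sign or symptom if there is no diagnosis. Protocol 11.7 lists "Edema/fluid retention", shortness of breath and exertional dyspnoea as separate items common in this population.

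**Contrast.** SAP 12.3.1 gives transaminases, another recognised effect, eDISH plots and threshold tables.

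**The concern.** The protocol singles out a risk with a characteristic time course and designs monitoring around it, but the final analysis has no output shaped to that risk. Two things can blur an early excess. One clinical picture may be recorded as fluid overload, oedema, dyspnoea or heart failure, and no rule counts a patient once across those terms. Events from the first weeks also share a row with events from the following five to six months.

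At stake is how well the study report can say whether the early risk seen in advanced CKD carries over to CTD-PAH patients. The question is worth settling because the risk has not been seen in PAH so far. If the grouping is left until the data are unblinded, a reader cannot tell whether the terms and interval were chosen to suit the result. SAP section 1 already classes analyses added after database lock as ad hoc.

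**Working it through.** The documents give no event rate, expected count or power for these events, so there is no figure of theirs to reproduce. Step 1 uses document figures only. Steps 2 to 4 are illustrations.

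**1. Share of the window after the risk period.** Patients "receive either placebo or bardoxolone methyl administered once daily for 24 weeks" (SAP 2.2), which is 24 × 7 = 168 days. Adding 30 days gives 198 days for a completer. The first three to four weeks are 21/198 = 10.6% to 28/198 = 14.1%. So 85.9–89.4% of the counting window lies after the period named in Protocol 5.1.2.

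**2. Effect of pooling over time.** From SAP Appendix B.2: 65 patients per arm. Assumed: risk in the first 4 weeks 15% active vs 2% placebo; then 1.5% per 4-week interval in both arms for six more intervals (28 weeks, 196 days).

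Whole-window risk = 1 − (1 − early risk) × (1 − 0.015)^6, and 0.985^6 = 0.9133.
- Active: 1 − 0.85 × 0.9133 = 22.4%, or 14.5 of 65 patients.
- Placebo: 1 − 0.98 × 0.9133 = 10.5%, or 6.8 of 65 patients.
- Early risk ratio: 15/2 = 7.5. Whole-window ratio: 22.4/10.5 = 2.1.

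**3. Effect of splitting over terms.** Spread evenly over 4 to 6 terms, each row averages 14.5/4 = 3.6 down to 14.5/6 = 2.4 active patients, against 6.8/4 = 1.7 down to 6.8/6 = 1.1 on placebo.

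**4. How often a row would stand out.** I simulated 20,000 trials per setting, taking each patient's first event and assigning it to a term with equal probability. The yardstick is a two-sided Fisher exact p ≤ 0.05.

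| Early risk, active vs placebo | Grouped, first 4 weeks | Grouped, whole window | Any single PT row (4–6 terms) |
|---|---|---|---|
| 10% vs 2% | 32% | 15–16% | 3–6% |
| 15% vs 2% | about 70% | about 36% | 7–14% |
| 20% vs 2% | 91% | 60–61% | 15–26% |

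A different set of assumptions gives the same direction: 15% vs 3% early, 10% later background in each arm, five terms. Whole-window risks are 1 − 0.85 × 0.90 = 23.5% and 1 − 0.97 × 0.90 = 12.7%, so the risk ratio falls from 5.0 to 1.85. Exact Fisher power is 57% for the early grouped count, 28% for the grouped count over the whole window, and 2% for one given PT row (7% with three terms).

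SOC rows and serious-event tables were not modelled. SOC rows would recover part of what is lost when terms share a class.

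**5. Other planned outputs.**
- Clinic weight is summarised by arm and visit (SAP 12.5). A mean can hide a few large gains, and Protocol 5.1.5 reports a mean loss of about 3 kg versus placebo at Week 16 in PAH patients, which pulls the other way.
- The discontinuation tables concern leaving the study. Protocol 8.4.1 asks patients who stop drug to stay in it, so a fluid event that ended treatment need not appear there.
- SAP 10.3 and 11.3 are redacted and cannot be checked; their headings are exploratory efficacy.

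**The case against.** **More is planned than preferred-term rows.** A reader might infer that these events are tabulated only by single term. SAP 12.2 itself shows otherwise: there are SOC rows with each patient counted once, serious-event tables and listings. This stands. A SOC row is still not a fluid overload grouping, because it adds unrelated events and can miss related terms in other classes.

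**The risk is not established in this population.** A reader might take fluid overload as a known harm here. Protocol 5.1.2 does not support that: the timing comes from Stage 4 CKD, six earlier CKD studies did not show the excess, and neither has PAH experience. This trial also excludes the main risk factors. That stands, and it limits the urgency.

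**The Fisher figures use a yardstick the SAP does not.** The SAP plans no test on adverse events, and a medical reader looks across rows. In the 15% vs 2% setting, more rows lean towards active than towards placebo in about 90% of simulated trials. So it would be wrong to read the table above as power lost, or to say the planned tables would show nothing.

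**Coding may be tidier than assumed.** Recording one diagnosis and suppressing its accompanying symptoms consolidates terms, and Protocol 9.1.1 requires a documented fluid assessment after an early 2.3 kg gain. This reduces splitting by an unknown amount.

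**Later events may be signal.** The planned dose change at Week 4 could bring its own excess, which a model with equal later risk ignores. That is an argument for showing onset by interval.

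**Other safeguards exist.** The DSMB reviews unblinded safety data quarterly, Protocol 11.7 promises regular aggregate review of the listed events, BNP and NT-proBNP are drawn at the early visits, and SAP Appendix E admits further tests. This is surveillance and supporting data; none of it is a pre-specified final comparison of patients with events.

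**Conclusion.** The concern holds in a limited form. SAP 12.2 lacks a grouped fluid overload / heart failure category and any summary by time of onset, while Protocol 5.1.2 and 9.1.1 treat the early weeks as the period to watch. The planned tables are therefore a weak basis for judging this risk.

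Only the window arithmetic is free of assumptions: 86–89% of a completer's counting window follows the three to four weeks in question. The direction of the loss follows from splitting and pooling. Its size depends on assumed rates, the number of terms, an even split and equal later risk. The illustrative 70%, 36% and 7–14% should be quoted only with those conditions.

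A reader might go further and conclude that the trial cannot answer the question. The documents do not support this: Protocol 11.6 collects onset dates, so the analysis can be done at any time. What is lost is pre-specification, not information. The change is worth making because it is cheap, and it has most value if made before unblinding.

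**What to change.** In SAP 12.2, before unblinding:

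1. Fix a MedDRA term list for a category named fluid overload / heart failure, and count each patient once across it.
2. Report by arm the patients with at least one event and with at least one serious event, with risk difference and 95% CI. A score-type interval suits the small counts.
3. Show first onset in Days 1–28, Days 29–56 (after the planned Week 4 dose change) and later, with a cumulative incidence plot from first dose. The Week 4 visit has a window of ±3 days, so the first boundary is approximate.
4. Add the number of patients per arm at or above the protocol's own 2.3 kg gain at each clinic visit, measured from Day 1 weight as in Protocol 9.1.1. The general SAP 5.1 baseline averages all pre-dose values and would not match.

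**Cost.** A term list, a few descriptive tables and one plot; no new data and no change to any clinical rule. Intervals will be wide. At 15% vs 2% with 65 per arm, the standard error is √(0.15 × 0.85/65 + 0.02 × 0.98/65) = 4.8 points, so a simple normal interval around 13 points runs from about 4 to 22. The tables should be presented as descriptive.

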8.4.1. Patient Discontinuation Criteria

Discontinuation refers to a patient's stopping administration of study drug. Reasons for study drug discontinuation may include the following:

- Confirmed clinical worsening event
- Occurrence of an AE or change in medical status that leads the investigator to be concerned about the patient's welfare
- Administrative reasons (*e.g.*, inability to continue)
- Sponsor termination of the study
- Voluntary withdrawal
- Females who become pregnant during the study
- Investigator unblinding

Patients must discontinue study drug if any of the following occur.

- ALT or AST > 8X ULN;
- ALT or AST > 5X ULN for 14 days;
- ALT or AST > 3X ULN and (total bilirubin > 2X ULN or INR > 1.5);
- ALT or AST > 3X ULN with the appearance of fatigue, nausea, vomiting, right upper quadrant pain or tenderness, fever, rash, and/or eosinophilia (> 5%);

Patients who are discontinued from study drug should still continue in the study, completing all study visits and undergo all scheduled study assessments, if possible.

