2.2.2. Discontinuation and termination of study patients

Patients may discontinue study drug or withdraw from the study at any time for any reason. Additionally, the sponsor reserves the right to terminate the study, and the investigator may discontinue an individual patient from study drug. Consultation with the medical monitor should occur before discontinuing study drug or withdrawing a patient from the study. The reason for a patient's discontinuation from study drug or study termination will be recorded in the electronic case report form (eCRF).

Patients who discontinue study drug should remain in the study and undergo all scheduled assessments, if possible. Patients who terminate from the study prior to the Week 24 study visit should be brought back to the clinic as soon as possible for early termination assessments (i.e., Week 24 Day Prior, and end-of-treatment visits) as well as a follow-up visit four weeks later. Patients should complete the end-of-treatment procedures, including the 6MWT, prior to any adjustments being made to their PAH treatment regimen.

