5.2.3. Last clinic visit and post-treatment results

Patients who terminate from the study before the Week 24 study visit should be brought back to the clinic as soon as possible for early termination assessments as well as a follow-up visit four weeks later. All assessments through Week 24 will be classified according to the time relative to randomization, regardless of the patient’s study participation or study drug status. Post treatment assessments will be classified according to the time relative to last dose in [Appendix D](#), for example 4 weeks off-treatment is within 7 to 35 days after last dose of the study.

Patients who discontinue treatment early but continue to be followed until the end of study will have their assessments attributed to visits as specified in [Section 5.2.1](#) and [Section 5.2.2](#).

A listing will indicate when each patient’s visits occurred. [Appendix D](#) indicates how scheduled results will be classified.

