7.2. Disposition

The disposition of patients (number randomized, study drug exposure, duration of follow-up, and inclusion in the various study populations) will be tabulated by treatment group in the ITT and Safety populations. Completion of study treatment, completion of study, discontinuation of study drug, discontinuation of study, and reason for discontinuation of study drug treatment and study will be summarized. See Section 8.2 for other summaries of treatment exposure. Time to permanent study drug discontinuation will be summarized. If the treatment end date or study end date are missing, the date will be imputed as the Study Drug Termination (SDT). If the treatment end date or study end date are missing and no reason for treatment or study discontinuation are included in the CRF, the reason for treatment or study discontinuation will be study termination.

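### SAP 12.2 ties its three 'leading to' AE outputs to study discontinuation, which, as SAP 7.2 uses the term, leaves out AEs that stop study drug in patients who stay in follow-up

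*SAP*

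**What the plan says.** SAP 12.2 uses the term *study discontinuation* in three places: a row in the overall summary of treatment-emergent adverse events (TEAEs), the incidence tables by system organ class (SOC) and preferred term (PT), and a listing. For the incidence tables it says: "The incidence of serious TEAEs and TEAEs leading to study discontinuation will be summarized in a similar manner". The section does not define the term, and no visible SAP text plans an adverse event (AE) table or listing for events leading to discontinuation of study drug.

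Elsewhere the documents keep the two outcomes apart. SAP 7.2 (Disposition) says that "discontinuation of study drug, discontinuation of study, and reason for discontinuation of study drug treatment and study will be summarized". Its rule for missing information reads: "no reason for treatment or study discontinuation are included in the CRF, the reason for treatment or study discontinuation will be study termination". Protocol 8.4.1 defines discontinuation as stopping study drug, and Protocol 8.4.2 defines termination as stopping drug together with all visits and assessments. Among the reasons for stopping drug, Protocol 8.4.1 lists "Occurrence of an AE or change in medical status that leads the investigator to be concerned". The reasons for termination in Protocol 8.4.2 are loss to follow-up, death and withdrawal of consent.

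Both documents want follow-up to continue after drug is stopped. Protocol 8.4.1: "Patients who are discontinued from study drug should still continue in the study, completing all study visits and undergo all scheduled study assessments, if possible". SAP 2.2.2: "Patients who discontinue study drug should remain in the study and undergo all scheduled assessments, if possible". SAP 5.2.3 sets visit rules for "Patients who discontinue treatment early but continue to be followed until the end of study".

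**The concern.** The AEs that make patients stop a drug are a core part of its tolerability profile, and safety relative to placebo is the protocol's secondary objective. The design creates the group at risk of being missed: an AE is a reason to stop drug, and the patient is then asked to stay. If the three outputs are programmed on leaving the study, such a patient contributes to none of them. The event would still be in the overall TEAE tables, and in the serious or fatal outputs if it qualified, but nothing there would mark it as the reason for stopping drug. A reader could not see, by arm and by SOC and PT, which events ended treatment.

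No efficacy analysis is touched.

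**Working it through.** The plan states no figure to reproduce, so the check is a comparison of wording, followed by the effect of one omitted patient.

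**1. Wording of the outputs (SAP 12.2).**

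| Output | Tied to study discontinuation | Tied to stopping study drug |
|---|---|---|
| Overall summary row | yes | no |
| Incidence by SOC and by SOC/PT | yes | no |
| Listing | yes | no |

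Three of three use study discontinuation; none uses study drug discontinuation.

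**2. Use of the exact term in the SAP.** It occurs five times in the visible text: three in SAP 12.2 and two in SAP 7.2. Both uses in SAP 7.2 set *study* against *treatment*, so there it means leaving the study. SAP 10.2 does name the other outcome in full when it deals with a patient who stops study drug because of an AE. SAP 12.2 does not.

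**3. The same patient under each reading.** Take a patient who stops drug for an AE at Week 6 (a week chosen for illustration) and attends every visit through Week 28.

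- If the term means stopping drug, the patient is in all three outputs.
- If it means leaving the study, the patient is in none.

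Because Protocol 8.4.2 names no AE reason for termination, the second reading could leave the three outputs nearly empty apart from deaths, which already have their own row and listing.

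**4. Whether another output fills the gap.**

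- SAP 7.2 summarizes reasons for stopping drug. This can give a count of AE-related stops by arm, but no SOC or PT.
- SAP 12.3.1 counts patients who cross liver-test thresholds. It does not count drug stops and covers only liver tests.
- SAP 12.2 repeats the TEAE analyses for off-treatment AEs. These start more than 30 days after the last dose, so they cannot have caused the stop.

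None of these gives AEs that stopped drug by SOC/PT or as a listing.

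**5. Effect of one omitted patient.** The change in an arm's percentage is 1/n, where n is the number of dosed patients in the arm. This assumes that all randomized patients are dosed.

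- 130 patients, 65 per group (SAP Appendix B.2): 1/65 = 1.54 percentage points.
- 200 patients (the upper limit), 1:1, so 100 per group: 1/100 = 1.00 percentage point.

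The documents give no rate of drug stops for AEs with continued follow-up, so the total cannot be calculated.

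**The case against.** The strongest reply is that SAP 12.2 already means stopping drug. Protocol 8.4.1 contains the only express definition of discontinuation in the documents, and it refers to drug; leaving the study is called termination. SAP 2.2.2 keeps the same pair of terms. An AE is a listed reason only for stopping drug, so the other reading gives nearly empty tables, which the authors are unlikely to have wanted. SAP 7.2 is also a weak guide to meaning: it uses *termination* loosely for study drug and gives study termination as a default reason for stopping treatment. In addition, all TEAEs are tabulated, reasons for stopping drug are summarized, and the underlying data are collected, so nothing is lost for good.

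Much of this stands. The drug reading may well be the intended one, and the defect may be no more than loose wording. But SAP 7.2 points the other way, SAP 12.2 leaves the term undefined, and SAP Section 1 makes the SAP govern over the protocol on planned analyses. A programmer who follows the SAP's own usage would produce the outputs that omit these patients. The reply also leaves one gap: no other visible output gives the SOC/PT breakdown or listing of AEs that stopped drug.

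It is also fair to say that 1/65 and 1/100 are the share of any single patient in any table. They show scale and do not estimate bias or a difference between arms.

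**Conclusion.** The concern holds. All three outputs are tied to study discontinuation, and as SAP 7.2 uses that term they omit AEs that stop study drug in patients who remain in the study. Confidence that this is the intended meaning is only medium, because the protocol's definitions support the other reading. The SAP needs correcting in either case, since two competent programmers could produce different safety tables from the same data.

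The effect is confined to descriptive safety output. It amounts to 1.5 points per omitted patient at 65 per arm or 1.0 point at 100 per arm, if all randomized patients are dosed; the number of such patients is unknown. The change should be made, but it does not threaten the trial's main conclusion.

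**What to change.** In SAP 12.2, define the overall row, the SOC and SOC/PT incidence tables and the listing on TEAEs leading to permanent discontinuation of study drug. Report TEAEs leading to study termination as a separate row.

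Derive the flag from the action taken for each AE (Protocol 11.6) and the recorded reason for stopping. SAP 2.2.2 says the reason for "discontinuation from study drug or study termination will be recorded in the electronic case report form (eCRF"). This assumes that the action-taken field records withdrawal of drug; the eCRF is not among the documents. If the field does not record it, the SAP should state how an AE is linked to the stop.

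For off-treatment AEs, drop only the drug-discontinuation outputs and keep all the other analyses that SAP 12.2 requires for them.

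The cost is a wording change in the SAP, one extra flag and one set of descriptive tables. Provided the eCRF assumption holds, no new data collection is needed.
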